3.3 Visit 2 (Treatment Periods 1, 2, and 3)

3.3.1 Period 1

Subjects will report to the CRU on the morning of Day 1.

3.3.1.1 Day 1

- Review of medical history;
- Review of medications and supplements;
- Measurement of vital signs (weight, seated SBP/DPB, and heart rate);

- Provide the first dose of single-blind placebo at least 45 minutes prior to breakfast;
- Provide breakfast;
- Subjects will be fitted with the continuous glucose monitoring (CGM) device and data recording will begin;
- Provide 4 doses (8 capsules) of single-blind placebo and instruct subjects to take one dose at least 45 minutes before lunch, one dose at bedtime, one dose at least 45 minutes before breakfast on Day 2, and one dose at least 45 minutes before lunch on Day 2.
- Adverse events will be monitored and recorded.
- Subjects will be instructed to return to the CRU at approximately 5pm (± 30 minutes) on Day 2.

3.3.1.2 Day 2

- Admission to the CRU at approximately 5pm (± 30 minutes);
- Review of medications and supplements;
- Measurement of vital signs (weight, seated SBP/DPB, heart rate, and temperature);
- Perform breathalyzer;
- Collect a urine sample for:
 - Drug screen;
 - Pregnancy testing (WCBP only)
- Provide a standardized diabetic meal at approximately 7pm (± 60 minutes). Standardized meals will continue throughout the remainder of the study Period.
- Provide a dose of single-blind placebo at approximately 10pm (± 60 minutes).
- Continue CGM monitoring;
- Adverse events will be monitored and recorded.

3.3.1.3 Day 3

- Review of medications and supplements;
- Measurement of vital signs (weight, seated SBP/DPB, heart and rate);
- Provide a dose of single-blind placebo at approximately 7am (± 60 minutes);
- Provide breakfast no sooner than 45 minutes after the morning dose;
- Provide a dose of single-blind placebo at approximately 1pm (± 60 minutes), at least 45 minutes prior to lunch;
- Provide lunch no sooner than 45 minutes after the afternoon dose;

- Provide dinner at approximately 7pm (\pm 60 minutes);
- Provide a dose of single-blind placebo at approximately 10pm (\pm 60 minutes);
- Collect a blood sample according to schedule (per randomization scheme, either morning, afternoon, or evening) prior to the specified dose of placebo for:
 - Pre-dose PD analysis
 - Serum chemistry
- Collect scheduled (per randomization scheme) postdose PD blood draws every 30 minutes (\pm 5 minutes) until 5 hours has elapsed;

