- Replace the CGM cannula at approximately 7pm (\pm 60 minutes), such that it does not interfere with any post-dose PD blood draws;
- Adverse events will be monitored and recorded.

3.3.1.4 Day 4

- Review of medications and supplements;
- Measurement of vital signs (weight, seated SBP/DPB, and heart rate);
- Randomization
- Provide a dose of study treatment or placebo at approximately 7am (\pm 60 minutes);
- Provide breakfast no sooner than 45 minutes after the morning dose;
- Provide a dose of study treatment or placebo at approximately 1pm (\pm 60 minutes), at least 45 minutes prior to lunch;
- Provide lunch no sooner than 45 minutes after the afternoon dose;
- Provide dinner at approximately 7pm (\pm 60 minutes);
- Provide a dose of study treatment or placebo at approximately 10pm (\pm 60 minutes);
- Continue CGM monitoring;
- Adverse events will be monitored and recorded.

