8.3 Continuous Glucose Monitor Evaluation

For the purpose of analysis:

- 24-hour will be considered to be from 6AM to 6AM,
- Daytime will be considered to be from 6AM to 10PM, and
- Nighttime will be considered to be from 10PM to 6AM.

The last 2 days with at least 80% of expected measurements prior to dosing will be considered the run-in days for each of the parameters. The last 2 days with at least 80% of expected measurements prior to 8 hours after the last dose will be considered the on treatment days. The measurements more than 8 hours after the last dose will be considered the follow-up days.

The area under the curve (AUC) will be derived for each of the time periods (24-hour, daytime and nighttime) using the indicated days (run-in days, treatment days and follow-up days). The average glucose measurement will be derived by dividing the AUC by the number of observed hours. The average change from run-in will be derived for each treatment regimen for both the treatment days and the follow-up days.

The placebo adjusted change in means will be derived for each of the active therapy regimens by subtracting the placebo mean (the mean change from run-in while the subject was receiving placebo) from the active therapy mean (the mean change from run-in while the subject was receiving the active therapy). The placebo adjusted change in means will be derived for both the treatment days and the follow-up days.

The placebo adjusted change in means will be analyzed using an Analysis of Variance (ANOVA) with treatment as the main effect to determine whether multiple doses a day has an effect on the CGM parameters.

The ratios of the placebo adjusted change in means between the active treatments within each subject will also be derived to estimate the magnitude of the dose response.

Summary statistics will be presented for both the placebo adjusted change in means and the ratios of the placebo adjusted change in means. Analysis results will be presented for the change in means.

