1.2. Study Overview

This a phase 2a, randomized, double-blind, double-dummy, placebo-controlled, 3-way crossover study enrolling approximately 30 adult subjects with T2DM from age 20 to 75 inclusive. Following a 7-10 day Screening period, eligible subjects will be housed in the CRU for the duration of each treatment cycle beginning with a 3-day single-blind placebo run-in. On Day 4, each subject will be randomized to a treatment sequence that will include three treatment assignments for each of three treatment periods according to the randomization scheme.

All eligible subjects will receive placebo plus two of the following: ORMD-0801 460 IU qd, OMRD-0801 bid, or ORMD-0801 tid. Subjects will receive the randomized treatment from Day 4 through Day 8. A 24-hour single-blind placebo washout will be done on Day 9. Subjects will be discharged on the morning of day 10. Each treatment Period will be separated by a 2-week washout. A final follow-up visit will be performed 1 week after the end of the third treatment period.

In addition, adverse events, clinical laboratory values, vital signs, and electrocardiograms (ECGs) will be evaluated periodically for safety.

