1.3. Study Objectives

1.3.1 Primary Objectives

The primary objectives of this study are to compare pre-treatment (Day 3) to end of treatment (Day 8) 24-hour CGM glucose for single and multiple doses of ORMD-0801 vs placebo and to evaluate safety parameters for single and multiple dose of ORMD-0801 vs placebo.

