2.8. Efficacy Evaluations

2.8.1. Continuous Glucose Monitoring

The last 2 days with at least 80% of expected measurements prior to dosing will be considered the run-in days for each of the parameters. The last 2 days with at least 80% of expected measurements prior to 8 hours after the last dose will be considered the on treatment days. The measurements more than 8 hours after the last dose will be considered the follow-up days.

The 24-hr period (6AM to 6AM), nighttime (from 10pm to 6am), daytime (6AM to 10PM), and post-prandial (first hour after meal start time including breakfast, lunch, and dinner) glucose values will be summarized. The mean, standard deviation, minimum, maximum, first quartile, median, third quartile and inner-quartile range will be presented.

The area under the curve (AUC) will be derived for each of the time periods (24-hour, daytime and nighttime) using the indicated days (run-in days, treatment days and follow-up days). The average glucose measurement will be derived by dividing the AUC by the number of observed hours. The average change from run-in will be derived for each treatment regimen for both the treatment days and the follow-up days.

The placebo adjusted change in means will be derived for each of the active therapy regimens by subtracting the placebo mean (the mean change from run-in while the subject was receiving placebo) from the active therapy mean (the mean change from run-in while the subject was receiving the active therapy).

The placebo adjusted change in means will be derived for both the treatment days and the follow-up days. The placebo adjusted change in means will be analyzed using an Analysis of Variance (ANOVA) with treatment as the main effect to determine whether multiple doses a day has an effect on the CGM parameters. If the residuals are not normally distributed, then a Kruskal-Wallis test (one-way analysis of variance on the ranks) will be performed.

The ratios of the placebo adjusted change in means between the active treatments within each subject will also be derived to estimate the magnitude of the dose response.

Summary statistics will be presented for both the placebo adjusted change in means and the ratios of the placebo adjusted change in means. Analysis results will be presented for the change in means.

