2.11. Sample Size and Power Considerations

A total of 30 subjects will be randomized to receive either placebo, ORMD-0801 460 IU qd, ORMD-0801 460 IU bid, or ORMD-0801 460 IU tid during each treatment period.

This study is not powered for statistical significance.

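### The CGM change score subtracts the whole run-in mean in both periods; using that mean as a covariate would probably give tighter 24-hour and daytime estimates at almost no cost.

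*SAP*

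**What the plan says.** The first primary objective is to "compare pre-treatment (Day 3) to end of treatment (Day 8) 24-hour CGM glucose for single and multiple doses of ORMD-0801 vs placebo" (SAP 1.3.1).

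The derivation has three steps, worded alike in Protocol 8.3 and SAP 2.8.1:

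- A change from run-in is formed in each period: "The average change from run-in will be derived for each treatment regimen for both the treatment days and the follow-up days".
- The placebo-period change is removed within subject, "by subtracting the placebo mean (the mean change from run-in while the subject was receiving placebo) from the active therapy mean".
- The result goes into a one-factor model: "The placebo adjusted change in means will be analyzed using an Analysis of Variance (ANOVA) with treatment as the main effect".

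Neither document names a run-in covariate. A run-in mean is nevertheless collected in every period.

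On size, SAP 2.11 says "A total of 30 subjects will be randomized to receive either placebo" or one of the three regimens in each period, and declares the study not powered. SAP 1.2 says "All eligible subjects will receive placebo plus two of the following" active regimens. The documents give no SD, correlation or effect size for CGM.

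Two entries in the Protocol 3.3 schedule matter here: on Day 2, "Admission to the CRU at approximately 5pm"; on Day 3, "Replace the CGM cannula at approximately 7pm".

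**The concern.** Each analysed value combines four period means: (on-treatment minus run-in) on active, minus (on-treatment minus run-in) on placebo. In a parallel-group trial, subtracting baseline removes stable differences between subjects. Here the within-subject comparison has already removed them. What is left in a period's run-in mean is useful only as far as it predicts the same subject's on-treatment mean in that period. Subtracting it in full is optimal only when that slope is 1. With a smaller slope, full subtraction adds run-in noise from two periods to the estimate.

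Precision is what is at stake. With about 20 subjects per active regimen and no power claim, the value of the CGM results depends on how tightly each regimen-versus-placebo difference is estimated. The 24-hour, daytime, nighttime and follow-up endpoints are all built this way.

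**Working it through.** The plan states no figure for precision, so there is nothing to reproduce. The check has four steps.

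**1. Inputs**

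- Subjects: 30 (SAP 2.11). Each receives placebo and two of three regimens (SAP 1.2), so 30 × 2/3 = 20 per regimen. This assumes balanced pairs; the allocation is in a separate randomization plan.
- Rho, the within-subject, period-level correlation of run-in and on-treatment means: not given, assumed.
- s, the run-in SD divided by the on-treatment SD on the same within-subject scale: not given, assumed.

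**2. Is a slope of 1 likely?**

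The analysis day runs from 6AM to 6AM. If Days 2-3 qualify as the run-in days, the window is 6AM Day 2 to 6AM Day 4. Using nominal clock times:

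| Endpoint | Run-in hours | Before 5pm admission on Day 2 | Before cannula change at 7pm on Day 3 |
|---|---|---|---|
| 24-hour | 48 | 11 | 24 + 13 = 37 |
| Daytime (6AM-10PM) | 32 | 11 | 16 + 13 = 29 |
| Nighttime (10PM-6AM) | 16 | 0 | 8 |

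On-treatment hours (Days 7-8 if complete) are all in the unit, on standardized meals and after the cannula change. For the 24-hour and daytime endpoints, the run-in is therefore measured partly at home and mostly before the cannula change. Both features plausibly lower rho and raise s. For nighttime, no run-in hours are at home and 8 of 16 follow the cannula change, so the argument is weaker.

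**3. Formula**

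Let σ be the on-treatment SD and n the number of subjects contributing to a comparison.

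- Double change score: variance = 2σ²(1 + s² − 2·rho·s)/n.
- Run-in as covariate, slope known: variance = 2σ²(1 − rho²)/n.
- Ratio = (1 + s² − 2·rho·s)/(1 − rho²), which is 2/(1 + rho) when s = 1. The best slope is rho/s.

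For example, with s = 1 and rho = 0.5, (1 + 1 − 1)/(1 − 0.25) = 1.33. With s = 0.8 and rho = 0.7, (1 + 0.64 − 1.12)/(1 − 0.49) = 0.52/0.51 = 1.02.

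The change score is worse than ignoring the run-in altogether when rho < s/2. At s = 1, rho = 0.3 and n = 20, its SE is √(4 × 0.7/20) = 0.374σ, against √(2/20) = 0.316σ without the run-in.

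**4. Simulation**

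The formula omits the cost of estimating the slope. The design was therefore simulated: 30 subjects, 10 per regimen pair, three periods, fixed subject, period and treatment effects for both responses, one shared slope, 4,000 trials per setting. Repeat runs differ by up to about 0.07. Variance ratios, formula / simulated:

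| s | rho 0.2 | rho 0.5 | rho 0.7 | rho 0.9 |
|---|---|---|---|---|
| 0.8 | 1.38 / 1.36 | 1.12 / 1.10 | 1.02 / 0.99 | 1.05 / 1.03 |
| 0.9 | 1.51 / not run | 1.21 / 1.20 | 1.08 / 1.06 | 1.00 / 0.98 |
| 1 | 1.67 / 1.62 | 1.33 / 1.30 | 1.18 / 1.16 | 1.05 / 1.03 |
| 1.25 | 2.15 / 2.14 | 1.75 / 1.71 | 1.59 / 1.60 | 1.64 / 1.62 |

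The square root of the ratio gives the relative interval width. At s = 1 the simulated values give √1.62 = 1.27, √1.30 = 1.14, √1.16 = 1.08 and √1.03 = 1.015. Intervals are thus about 27%, 14%, 8% and 1.5% wider.

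A separate slope for each regimen would cost more. With n = 20 and s = 1 the covariate variance is multiplied by 1 + 1/17, and break-even falls at rho = 2/(1 + 1/17) − 1 = 0.89. This is the reason to fit one shared slope.

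**The case against.** The strongest reply is that this is an efficiency preference of unknown size. The objective is itself a pre-treatment to end-of-treatment comparison, and a change from run-in answers it directly. Periods are separated by two weeks at home, so drift shared by the run-in and treatment days of one period would raise rho; that is a good reason to use a period-specific baseline. On-treatment means on active may also carry between-subject variation in drug response that placebo run-in means do not, so s below 1 is possible. There the gain can vanish, as the first two rows of the simulation table show. All of this stands, and it limits how large a loss can be claimed.

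The hours at home also depend on the Protocol 3.3 schedule. SAP 1.2 reads as if subjects are housed from the start of the run-in. If that were so, the 11 hours would drop out, but the 37 hours before the cannula change would remain.

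A reader might go further and infer any of the following. The documents support none of them.

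- Every regimen-versus-placebo estimate loses precision. This needs a slope away from 1 for every endpoint, and no rho or SD is given.
- The covariate analysis can never be worse. With s = 0.9 and rho = 0.9 the simulated ratio is 0.98.
- The planned estimate is biased. With randomized sequences, and no carryover into later run-ins, both estimators target the same difference.
- The sample size or power is wrong. The study is declared not powered, so no such figure is affected.

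Finally, the simulation fits subject, period and treatment to both responses, whereas the SAP names treatment only. The ratios isolate the choice of response and do not measure the whole difference from the planned ANOVA.

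**Conclusion.** The point holds as a conditional loss of precision. The plan fixes the run-in weight at 1 in both periods, and this is inefficient whenever the within-subject slope is clearly below 1. The schedule makes that plausible for the 24-hour and daytime endpoints and gives weaker grounds for nighttime.

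The loss ranges from nothing to roughly a doubling of variance over the assumed values of rho and s. With equal SDs it runs from about 60% extra variance at rho 0.2 to about 3% at rho 0.9. The case for changing rests on the asymmetry: the gain may be substantial, while the worst case found was a variance loss of about 2%. The assumptions are balanced regimen pairs, Days 2-3 as run-in days, and one slope common to all regimens.

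**What to change.** In SAP 2.8.1 and Protocol 8.3:

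- Make each period's on-treatment mean the response, or its follow-up mean for the follow-up endpoint.
- Fit subject as a fixed effect, period, treatment (placebo and the three regimens) and that period's run-in mean, with one shared slope. The fixed subject effect makes the slope a within-subject one.
- Report adjusted regimen-minus-placebo differences with 95% CIs for 24-hour, daytime, nighttime and follow-up glucose.
- Keep the double change score as a descriptive summary.

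The cost is wording in two documents and a few lines of SAS, with no new data. The slope takes one degree of freedom. The subject and period terms, which bring the placebo periods into the model, are a further change and should be stated as such. The Kruskal-Wallis fallback in SAP 2.8.1 carries no covariate or subject term, so the handling of non-normal residuals would need restating. If the true slope is near 1, the variance may rise by about 2%.

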Except in cases of emergency, the Investigator should consult with the Sponsor and the Medical Monitor before removing the subject from the study. In some circumstances it may be necessary to temporarily interrupt treatment as a result of AEs that may have an unclear relationship to study treatment. The Investigator should obtain approval from the Sponsor and Medical Monitor before restarting study treatments that were temporarily discontinued for an AE.

In the event that a subject discontinues the study prior to completion, the date the subject is withdrawn and the reason for discontinuation will be recorded in the source documents and CRF. Although a subject will not be obliged to give his/her reason for withdrawing prematurely, the Investigator will make a reasonable effort to obtain the reason while fully respecting the subject's rights.

All subjects who are randomized and treated (i.e., received any amount of study treatment) will be included in the safety analyses. Thus, every effort will be made to contact any subject who fails to attend any follow-up appointments/contacts, in order to ensure that he/she is in satisfactory health. If a subject withdraws from the study as a result of meeting discontinuation criteria after the start of study treatment administration, reasonable efforts should be made to have the subject return for the early withdrawal evaluations (Section 3.5). Any subject withdrawn due to a suspected study treatment -related AE should be followed until resolution or stabilization of the event.

If a subject becomes pregnant, study treatment will be discontinued immediately, and the subject will be referred to an obstetrician/gynecologist experienced in reproductive toxicity for further evaluation and counseling. The subject will be followed until delivery or other termination of pregnancy for outcome.

Subjects may choose to withdraw authorization to use and disclose their PHI as defined by the HIPAA. Such withdrawal of authorization must be made to the Investigator in writing. Any PHI collected by the Investigator prior to the date of such withdrawal will continue to be used and disclosed.

Randomized subjects who are discontinued from this study for any reason will not be replaced.

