2.2. Study Populations

Safety population: All patients who receive at least one dose of the study drug will be included in the safety population

Efficacy population: Intent-to-treat (ITT) population with last observation carried forward (LOCF) in patients who receive at least one treatment with study drug and in whom CGM data was collected at least once during treatment.

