2.13. Handling Missing Data

Listings will be provided for all data. Descriptive statistics will be provided for all planned visits as provided on the Case Report Forms (CRFs).

Study days will be analyzed using the study days as reported in the Case Report Form. Likewise, unscheduled visits will not be reassigned a visit number based on the visit date.

Dates related to the adverse events and medications will be imputed using the rules below in an effort to categorize them properly into the summary tables.

Imputing partial or missing start dates:

- If the year is unknown, then the start date will not be imputed. The date will remain missing.
- If the month is unknown and the year is the same as the first dose date of the study, then impute the month and day of the date to be equal to the first dose month and day. Otherwise, impute the month as January.
- If the day is unknown and the month and year are the same as the first dose date of the study, then impute the day to be equal to the day of the first dose. Otherwise, impute the day as '01'.

Impute partial or missing stop dates:

- If the year is unknown, then the stop date will not be imputed. The date will remain missing.
- If the month is unknown, impute the month as December.
- If the day is unknown, impute the day to be the last day of the month.

If an imputed stop date is greater than the date of study completion/discontinuation date of the study, then the imputed stop date will be set equal to the date of completion/discontinuation date.

The imputed dates will be stored in the analysis datasets along with the original dates as recorded by the sites.

Efficacy analyses will be performed for the ITT population in which CGM data was collected during treatment. The weighted mean night time glucose levels will be calculated on CGM data as described in Section 2.8.1. No imputation will be used other than application of linear interpolation for calculation of the trapezoidal areas.

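### The CGM ANOVA uses only active-minus-placebo differences, so a subject with no evaluable placebo period leaves it with all active-period data, although the contrast it tests needs no placebo value

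*SAP*

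**What the plan says.** Each subject receives placebo and two of the three active regimens over three periods. For each active regimen, SAP 2.8.1 derives a placebo-adjusted change by "subtracting the placebo mean (the mean change from run-in while the subject was receiving placebo) from the active therapy mean"; Protocol 8.3 has the same rule. This derived value is what gets tested: "The placebo adjusted change in means will be analyzed using an Analysis of Variance (ANOVA) with treatment as the main effect". The stated purpose of the test is to see whether dosing more than once a day matters, so it compares qd, bid and tid with one another. Within-subject ratios between the active regimens are formed from the same values.

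A period is evaluable if enough sensor days qualify. On treatment these are "The last 2 days with at least 80% of expected measurements prior to 8 hours after the last dose", and run-in has a matching two-day rule.

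On missing data the documents disagree. SAP 2.13 says "No imputation will be used other than application of linear interpolation for calculation of the trapezoidal areas", and Protocol 8.4.8 rules out substitution in any calculation. SAP 2.2, however, defines the efficacy population as "Intent-to-treat (ITT) population with last observation carried forward (LOCF) in patients who receive at least one treatment with study drug" with some on-treatment CGM data. Protocol 4.3 adds: "Randomized subjects who are discontinued from this study for any reason will not be replaced".

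**The concern.** The analysed variable does not exist without the subject's own placebo change. If placebo was never reached, or too few of its run-in or treatment days qualify, neither active period can enter the ANOVA or the ratios. Yet SAP 2.2 asks only for "patients who receive at least one treatment with study drug and in whom CGM data was collected at least once during treatment", so the subject remains in the efficacy population.

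The loss is avoidable. For a subject with active changes A1 and A2 and placebo change P, the active-versus-active contrast is (A1 − P) − (A2 − P) = A1 − A2. Placebo cancels, so a subject with both active periods and no placebo has fully observed the contrast under test and is still excluded.

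With 30 subjects and no replacement, precision is at stake. There is also a possible selection effect: when placebo comes late, whether a subject counts can depend on what happened on active treatment. Protocol 4.3 lists adverse events and hypoglycaemia among the reasons for stopping study drug.

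**Working it through.** The plan has no power figure to reproduce. Both documents give N = 30 without inputs and say that the study is not powered for significance.

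**Inputs from the documents.** 30 subjects with two active periods each: 60 placebo-adjusted values, 20 per regimen if balanced.

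**Assumed, because the documents are silent.** Placebo falls in each period for one third of subjects (randomization details are in a separate plan). Dropout is *h* at each transition between periods. A started period has unusable CGM data with probability *f*. Alpha is 0.05, two-sided.

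**Step 1: active records discarded.** Let r2 = 1 − h and r3 = (1 − h)².

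- Each period holds 20 active records, so active records collected = 20 × (1 + r2 + r3) × (1 − f).
- An active record is usable only if the later of its own period and the placebo period is reached and both are evaluable. With ten subjects per placebo position (first: r2 + r3; second: r2 + r3; third: 2·r3), usable records = 10 × (2·r2 + 4·r3) × (1 − f)².

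| h / f | Collected | Usable | Discarded |
|---|---|---|---|
| 10% / 0 | 20 × 2.71 = 54.2 | 10 × 5.04 = 50.4 | 3.8 (7.0%) |
| 5% / 5% | 20 × 2.8525 × 0.95 = 54.2 | 10 × 5.51 × 0.9025 = 49.7 | 4.5 (8.2%) |
| 10% / 10% | 20 × 2.71 × 0.90 = 48.8 | 10 × 5.04 × 0.81 = 40.8 | 8.0 (16.3%) |

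In the last row about 5.3 of the 30 subjects lose all their active data.

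**Step 2: power for equality of the active regimens.** By simulation, with assumed effects of 0.2, 0.7 and 1.2 within-subject SD for qd, bid and tid. The same subject + period + treatment model is fitted to all evaluable periods, and then only to subjects with an evaluable placebo period. The gap between the two isolates the placebo requirement.

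| h / f | All periods | Placebo required |
|---|---|---|
| 0 / 0 | 69% | 69% |
| 10% / 0 | 62% | 61% |
| 5% / 5% | 65% | 62% |
| 10% / 10% | 54% | 48% |

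A repeat of the last row gave 55% and 50%. For tid versus placebo the gap is only 0 to 2 points. For regimen versus placebo under random dropout, the paired standard error is about 1% larger than the mixed-model one at 5% dropout per period, and 6% larger at 20%.

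Neither column is the SAP's literal test. A one-way ANOVA on the placebo-adjusted values gives 46% with complete data and 29 to 31% at 10%/10%. Most of that shortfall comes from the model form, which is a separate matter and is not counted here.

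**Step 3: bias in regimen versus placebo.** By simulation, with a true effect of −15 mg/dL, assumed SDs of 20 mg/dL (subject, subject-by-active, residual) and about 10% leaving. The mixed model uses known variances.

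| Who leaves | Paired estimate | Mixed model, all periods |
|---|---|---|
| Strong observed responders, after an evaluable active period | −12.8 | −15.0 |
| Strong true (unobserved) responders | −12.6 | −14.0 |
| Strong responders, before evaluable active data | −11.9 | −12.2 |
| Weak responders, after an evaluable active period | −17.3 | −15.1 |

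The simulation SD of an estimate is about 6 over 1,500 runs, so Monte Carlo error is about 6/√1500 = 0.15. Purely random loss gives no bias.

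**The case against.** The case for leaving the plan alone has real content.

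- **No power is claimed.** This stands: the loss is one of precision. In the step 2 model, power falls from 69% to 54% at 10%/10% because records were never collected; the placebo requirement takes only the next 5 to 6 points.
- **The active data are not lost from all reporting.** This also stands. SAP 2.8.1 derives the change from run-in for each regimen, which needs no placebo period, and Table 14.2.1.1 is titled as a pre-treatment to end-of-treatment summary. A reader might infer that every ITT table is silently limited to subjects with placebo. The documents do not show that, and the table shells are in a separate file.
- **Sensor trouble during placebo need not remove anyone.** This stands in part. On treatment, two qualifying days out of five suffice. Run-in has less slack: the sensor is fitted after breakfast on Day 1 and the cannula is changed on Day 3, leaving at most three candidate days for the two required.
- **Bias toward zero rests on an assumed mechanism.** This stands. No withdrawal rate is given. The Protocol introduction reports two self-reported hypoglycaemia events in the six-week study, and Protocol 5.3.1.2 makes each dose conditional on a CGM reading. The direction reverses if weak responders leave.
- **The mixed model is shown at its best.** This is fair. Its variances were set to the true values, and it recovers the effect fully only when leaving depends on observed data. It barely helps when subjects stop before evaluable active data.
- **LOCF in SAP 2.2 might rescue the subject.** This fails. It contradicts SAP 2.13 and Protocol 8.4.8, and cannot supply a placebo value that was never observed. Carrying an active value into the placebo slot would be worse than exclusion.

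**Conclusion.** The point holds as a needless loss of observed data, of modest size. A subject without an evaluable placebo period leaves the CGM ANOVA and ratios, but not the per-regimen summaries. The cost is small at moderate loss and noticeable only when dropout and sensor failure are both about 10%. All loss rates, placebo positions, effects and SDs behind these figures are assumptions.

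A reader might infer that the plan attenuates the drug effect or leaves the trial underpowered. The documents support neither: they give no evidence on who leaves and set no power target. What can be said is conditional. Regimen-versus-placebo estimates are pulled toward zero if strong responders leave after an evaluable active period and before placebo, away from zero if weak responders do, and not at all if loss is random. Bias from subjects who stop before evaluable active data is not caused by the placebo subtraction.

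The conflict between SAP 2.2 and SAP 2.13 needs resolving in any case, because it leaves the handling of a missing placebo period open.

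**What to change.** In SAP 2.8.1 and Protocol 8.3:

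1. Analyse each subject's period-level change from run-in in one linear mixed model with treatment (placebo, qd, bid, tid), period and random subject, using every evaluable period.
2. Take the regimen-versus-placebo and active-versus-active estimates as contrasts from that model.
3. Keep the placebo-subtracted values and the ratios as descriptive summaries, labelled as evaluable pairs.
4. Report how many subjects lack an evaluable placebo period.
5. Remove the LOCF wording from SAP 2.2 so that it agrees with SAP 2.13 and Protocol 8.4.8.

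The rank-based fallback in SAP 2.8.1 was written for a one-way ANOVA and should be restated to match.

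The cost is SAP wording, a Protocol 8.3 change through the amendment procedure in Protocol Section 10, and one standard mixed-model call in the SAS already planned. No extra data or subjects are needed. The small downside is reliance on data missing at random and on a common between-period correlation. With no missing periods the model uses the same data as the present plan.
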